5.7.1.1 FDA-approved device being used in this research according to the approved labeling

1. GlideScope (<https://accessguidid.nlm.nih.gov/devices/00879123006400>)
2. Storz C-Mac (<https://accessguidid.nlm.nih.gov/devices/04048551409381>)
3. i-view (<https://www.intersurgical.com/content/files/108253/-1977057700>)

5.7.1.2 FDA-approved device being used in this research in a manner other than its approved labeling

N/A – This section is not applicable.

5.7.1.3 Any device not approved by the FDA

N/A – This section is not applicable.

B5.7.2 Drugs

B5.7.2.1 FDA-approved and used in accordance with the approved labeling

N/A – This section is not applicable.

B5.7.2.2 FDA-approved and used in a manner not in accordance with its approved labeling

N/A – This section is not applicable.

B5.7.2.3 Any drug not approved by the FDA

N/A – This section is not applicable.

B8 Statistical Analysis

B8.1 Sample Size Estimation

A power analysis in SAS version 9.4 (SAS Institute, Cary, NC) indicated that a total sample of 122 would be needed to find that the i-view is non-inferior to the reusable VL if the expected outcome rate (proportion of patients experiencing first-pass success) for the i-view is 87%, the expected outcome rate for the reusable VL is 92%, the noninferiority margin is 5%, power is 80%, and alpha is 5%.

B5.8.2 Data analysis

We will use the Farrington-Manning score test for non-inferiority to test the first two hypotheses (that the i-view has a non-inferior proportion of patients experiencing hypoxic events, and that the i-view has a non-inferior first-pass success rate compared to the reusable VL devices). The Farrington-Manning score test computes the proportion (risk) difference and 90% confidence interval (for a one-sided test) with regards to a predetermined non-inferiority limit. We will use pairwise deletion to handle missing data points (i.e., will only exclude observations if missing data relevant to the specific analysis). Moreover, we may perform regression modeling to adjust for confounders. We performed all statistical analysis using Microsoft Excel (version 10, Redmond, Washington) and JMP Statistical Discovery from SAS (version 13, Cary, NC) or another available commercial software package. We will present continuous variables as means and 95% confidence intervals, non-parametric continuous variables and ordinal variables as medians and interquartile ranges, and nominal variables as percentages and numbers. Significance will be set at $p=0.05$. We will compare binomial variables using the Chi-square test, normally distributed continuous variables using the Student's t-test, and non-parametric and ordinal variables using the Wilcoxon Rank sum test.

SECTION C: HUMAN RESEARCH PROTECTIONS

C1. RECRUITMENT AND CONSENT

C1.1 Identification and Selection of Subjects

Patients will not be specifically recruited for this study. The decision to perform an intubation using VL will be purely at the direction of the attending clinician.

C1.2 Recruitment Process

N/A – This section is not applicable.

C1.3 Eligibility

N/A – This section is not applicable.

C1.4 Consent Process

We are seeking a waiver of consent for this clinical rotating protocol as we have done with BAMC protocol C.2015.140. All the devices of interest in this study are already in use in the ED and, while we are seeking to establish a clinical rotating protocol, clinicians can always break the protocol if indicated per their discretion. The procedure itself – emergency intubation – does not normally require consent in the emergency setting.

C1.4.1 Research involving subjects with cognitive impairment or who lack capacity to provide informed consent

N/A – This section is not applicable.

C1.4.2 Research involving non-English speaking subjects

N/A – This section is not applicable.

C1.4.3 Research involving a waiver of the requirement to obtain informed consent OR alteration of the elements of informed consent

*The research involves no more than minimal risk to the subjects; and
The waiver or alteration will not adversely affect the rights and welfare of the subjects;*

We are seeking to capture data that is part of routine healthcare operations. The data that we are capturing represents data that is routine in the clinical setting and thus does not elevate the risk above that of routine patient care. The clinical rotating protocol is using devices that are already in use in the department, are being used for their FDA cleared indications, and are all considered technically equivalent devices. The intubation procedure itself is purely at the direction of the attending clinician.

The research could not practicably be carried out without the waiver or alteration;

We are specifically seeking out encounters in which an intubation occurs under this clinical rotating protocol. Intubations are only performed in patients that are critically ill and unable to participate in the consent process. We routinely perform these procedures without consent due to their underlying illness, and thus it would be impractical to attempt to consent them for the purpose of a clinical rotating protocol using devices that are already in use in the department. Moreover, attempting to consent them would result in delays in their care.

Whenever appropriate, the subjects will be provided with additional pertinent information after participation.

Many of the patients that we are intubating are critically ill and not expected to survive. As such, it would be impractical to attempt to provide them with information on a procedure that occurred as part of their routine clinical care.

C1.4.4 Research involving a waiver of the requirement for investigator to obtain a signed consent form

N/A – This section is not applicable.

C1.4.5 Waivers of assent or parental permission when the research involves children

N/A – This section is not applicable.

C1.4.6 Research involving data collection for the USAMRDC Volunteer Registry Database

N/A – This section is not applicable.

C2. COMPENSATION FOR PARTICIPATION

Patients will not be compensated for participation as we are only collecting data in conjunction with routine clinical care.

C3. WITHDRAWAL FROM RESEARCH PARTICIPATION

For the clinician centered data we do not anticipate any withdrawal from the study. We have been collecting data on airway interventions since 2015 as part of BAMC protocol C.2015.140 without any encounters for which a clinician asked that we cease data collection, declined participation, or asked that their data be withdrawn. However, in the event that a clinician asks to be withdrawn we will only use their CRFs that were collected up to that point. If a reason is provided, we will document such.

For the patient EMR-based data we do not anticipate any patient withdrawal as we are seeking a waiver of informed consent and HIPAA waiver and thus they will likely not be aware of the study. However, in the event that a patient does request withdrawal in writing to the PI or a study team member we will cease data collection from that point forward. Data that was already collected will still be retained for use. Since the overwhelming majority of our data comes from medical records review, we cannot make any changes, removal, or revisions to the data in the EMR system even if the patient were to request such.

C4. PRIVACY FOR SUBJECTS

We are not intending any direct interaction between study team members and subjects for the study with the exception of the clinical personnel. They may interact with the subjects only for routine healthcare and will not be for the purposes of this study. As we are requesting a HIPAA waiver and consent waiver, additional privacy for recruitment and such will not be required and standard measures for privacy will be maintained per usual methods for healthcare delivery. The data will be maintained and stored as outlined.

C5. CONFIDENTIALITY PROCEDURES FOR RESEARCH RECORDS, DATA, HUMAN BIOLOGICAL SPECIMENS

The hard-copy forms will be immediately deposited into a secured lock-box in the ED and destroyed by shredder once entered in the database(s). The data collection tool is password protected, encrypted. Regarding the component of the study using data to include the case report form, these will include minimal PHI in the form of a patient sticker that we routinely use for patient care labeling. The CRF data will be converted into an electronic database and linked with outcome data. Please see data variable collection appendix listed below. Data will be stored on a password-protected Excel database maintained on a government computer for the period of the study protocol. All of these forms will also be destroyed immediately after entry into the Excel database.

C6. RISKS OF HARM, MEASURES TO REDUCE THE RISKS OF HARM, AND BENEFITS OF PARTICIPATION

C6.1 Risks of Harm

No procedures or interventions are being performed because of this study. We are only seeking to answer a specific research question as part of a clinical rotating protocol using devices that are already in use and indicated for the same situations. While the critical nature of their illness and the mere need puts them at high risk as part of their routine medical care. We do not believe the use of a rotating protocol places them at additional risk. Moreover, clinicians can break the protocol if there is a specific clinical indication without any penalty.

C6.2 Incidental or Unexpected Findings

N/A – This section is not applicable. Unexpected or incidental findings are not expected as part of this study. If, in the unlikely event something is discovered, we will refer the information back to the primary attending clinician.

C6.3 Potential Benefits

The study subjects will experience no direct benefits as a result of participating in this study given that it is purely observational. That said, their participation will facilitate the informing of best intubation practice which could conceivably benefit them in the future should they again require emergency airway management.

C7. DATA AND SAFETY MONITORING

N/A – This section is not applicable.

C8. REPORTABLE EVENTS

C8.1 Expected adverse events

There are a multitude of expected events related to the intubation procedure that are all considered part of routine clinical care. Examples of such events include hypoxia, aspiration, dental or other oral injury, multiple intubation attempts, false intubation into the esophagus, injury from the device, infection, and other anatomical injuries. More severely, hypoxic events resulting in anoxic brain injury or peri-intubation cardiac arrest are also well-described events associated with intubation and are not expected to be a result of the research study.[11]

C8.2 Unexpected adverse events and unanticipated problems

We do not anticipate unexpected adverse events as the decision to intubate is purely at the direction of the attending clinician. The devices are already in use in the department and are being used in their FDA cleared manner. If an adverse event occurs specific to the research, the adverse event will be reported to the PI or a member of the study team. If the event is determined to be related to the research the PI will follow standard reporting procedures for reporting the even to the regulatory office. If in the event there is an unexpected adverse event and unanticipated problem, PI or research staff will report to ISR Research Regulatory Compliance Division (RRCD) by e-mail to [contact]. A complete written report will follow the initial notification.

C8.3 Adverse device effects

We do not anticipate adverse events that are specific to this clinical rotating protocol. As the devices in the protocol are already in use in the department, any device related malfunction or risks are similar to that associated with the procedure itself.

C8.4 FDA-regulated research under IND and IDE

N/A – This section is not applicable.

SECTION D: REFERENCES

1. April, M.D., et al., *Emergency Department Intubation Success With Succinylcholine Versus Rocuronium: A National Emergency Airway Registry Study*. Ann Emerg Med, 2018. **72**(6): p. 645-653.

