B4. OBJECTIVES/SPECIFIC AIMS/RESEARCH QUESTIONS

We are seeking to implement a clinical rotating protocol in which we will use alternating months for which VL device is to be used comparing the i-view to the reusable devices within our department.

We are seeking to answer the following questions:

- (1) Does the i-view have similar first pass success rates compared to the reusable VL devices (e.g. GlideScope, C-Mac)?
- (2) Does the i-view have similar attempts required for placement compared to the reusable VL devices?

B5. RESEARCH PLAN

B5.1 Research Design

We are seeking to conduct a **prospective study** comparing outcomes between the disposable i-view and our other reusable VL devices.

B5.2 Research Subjects/Population(s)

B5.2.1 Subject Population(s)

We are seeking all patients undergoing intubation for which the clinician **chooses** to use VL.

B5.2.2 Number of Subjects, Records, and/or Specimens

We are seeking all encounters for which a VL intubation happens over the course of 2 years. Our limit will be based on the number of times the procedure occurs. Based on previously published data, we are estimating ~200 intubations with 55% using VL per year based on our previous experience.[2]

B5.2.3 Inclusion Criteria

We are seeking any encounter for which the patient undergoes VL intubation as part of routine clinical care.

B5.2.4 Exclusion Criteria

No intubation will be excluded so long as VL is used.

B5.3 Research Procedures

Intubation Procedure	All intubations will be performed at the direction of the attending clinician. The decision to intubate is based purely on clinical factors by the primary team. The decision to use VL device will be at the direction of the clinical team. No patient will be recruited specific for this procedure.

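### B8.1 claims 80% power with 122 encounters, but its assumed 5-point i-view deficit equals the 5-point margin, so the chance of showing non-inferiority is about 5% at any sample size

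*Combined protocol and SAP*

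**What the plan says.** Section B8.1 (Sample Size Estimation) reports a SAS power analysis concluding that "a total sample of 122 would be needed to find that the i-view is non-inferior to the reusable VL". Its inputs are that "the expected outcome rate (proportion of patients experiencing first-pass success) for the i-view is 87"% and that "the expected outcome rate for the reusable VL is 92%, the noninferiority margin is 5%, power is 80%, and alpha is 5"%.

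Section B5.8.2 (Data analysis) names the test and scale: "The Farrington-Manning score test computes the proportion (risk) difference and 90% confidence interval (for a one-sided test"), judged against a pre-set limit. That means a one-sided 5% test on the absolute difference in proportions.

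The power statement serves the first research question in B4: "Does the i-view have similar first pass success rates compared to the reusable VL devices".

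Accrual is set separately. B5.2.2 says "We are seeking all encounters for which a VL intubation happens over the course of 2 years" and "Our limit will be based on the number of times the procedure occurs". On volume, "we are estimating ~200 intubations with 55% using VL per year based on our previous experience".

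**The concern.** A non-inferiority study is powered by the distance between the true difference assumed and the limit to be ruled out. First-pass success is a benefit, so the i-view is non-inferior if i-view minus reusable can be shown to exceed −5 points. B8.1 assumes that the true difference is −5 points. The distance is zero, and there is nothing for a larger sample to detect.

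B8.1 is the plan's only statement of power. If it is wrong, readers are told that 122 encounters can answer the first research question when the stated assumptions say that no number can. A failure to show non-inferiority could then be misread as evidence against the i-view from an adequately powered study.

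**Working it through.** **Inputs.** From B8.1: i-view rate pT = 0.87, reusable rate pC = 0.92, margin 0.05, power 80%, alpha 5%, total N = 122. From B5.8.2: Farrington-Manning score test on the risk difference, one-sided 5%. From B5.2.2: 200 × 55% = 110 VL intubations a year, so about 220 in two years. Months alternate between devices (B5.3), so equal arms are assumed: 61 per device at N = 122 and about 110 at N = 220. Month-level clustering is ignored.

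**Formulas.** With n per device and effect e = (pT − pC) + 0.05:

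- n = [(1.6449·s0 + 0.8416·s1) / e]²
- power = Φ[(e·√n − 1.6449·s0) / s1]
- s1 = √[pT(1 − pT) + pC(1 − pC)]
- s0 has the same form, using the restricted maximum-likelihood rates, which are forced to differ by exactly −5 points

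**1. The plan's figure from the plan's inputs.** e = (0.87 − 0.92) + 0.05 = 0, so n is infinite. The assumed rates already satisfy the restriction, so s0 = s1 = √(0.1131 + 0.0736) = 0.4321, and power = Φ(−1.6449) = 5.0% whatever n is. Exact enumeration of the score test gives 4.8% at 61 per device, 4.9% at 110 and 4.7% at 122. Splitting 122 as 41/81 or 81/41 gives 4.6% or 5.7%. The plan's 80% is not reproduced.

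**2. Other readings of the same inputs.**

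- *Relative margin.* 5% of 92% is 4.6 points, so the assumed 5-point deficit lies beyond the limit. Power is 4.3% at 61 per device and falls to 2.6% at 1,000.
- *Two-sided 5%, that is one-sided 2.5%.* Power at the limit becomes 2.5%.

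No variant that keeps the stated rates, direction and margin gives 122.

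**3. Where 122 does appear.** Exchange the rates (i-view 0.92, reusable 0.87). Then e = 0.10 and s1 = 0.4321 as before. The restricted rates are 0.8604 and 0.9104, so s0 = 0.4490.

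- n = [(1.6449 × 0.4490 + 0.8416 × 0.4321) / 0.10]² = (1.1022 / 0.10)² = 121.5, so 122 **per device**, 244 in total.
- At 61 per device: Φ[(0.7810 − 0.7386) / 0.4321] = 54%.
- At 110 per device: Φ[(1.0488 − 0.7386) / 0.4321] = 76% (exact 77%).
- At 122 per device: 80% (exact 81%).

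**4. Power at the expected accrual.** The equal-rate rows are illustrations, not assumptions of the plan.

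| True rates (i-view / reusable) | Power at 61 per device | Power at 110 per device | n per device for 80% |
|---|---|---|---|
| 87% / 92% (as stated) | 5% | 5% | none |
| 92% / 92% | 25% | 37% | 380 |
| 87% / 87% | 20% | 29% | 567 |
| 92% / 87% (reversed) | 54% | 76% | 122 |

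As an example, the 92%/92% row at 110 uses s0 = 0.3961 and s1 = 0.3837: Φ[(0.05 × 10.488 − 1.6449 × 0.3961) / 0.3837] = Φ(−0.33) = 37%.

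For about 80% power at 110 per device the i-view would have to be truly better: about 95.6% against 92%, or 92.4% against 87%.

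**The case against.** The best defence is that nothing in the conduct of the study depends on 122. It is neither a cap nor a stopping rule: every VL encounter in two years is taken, and the test, interval and data collection are unaffected in a study presented as minimal risk. That is true, and it limits the consequence to what the plan claims about itself. It does not rescue the claim, because more encounters add nothing when the assumed truth sits on the limit.

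A second defence is that the rates were simply transposed in the text. The agreement at 121.5 makes this plausible, but no software input is shown. Exchanged rates cannot be told apart from a wrong sign on the margin. Either would also need a per-device number to have been reported as a total, and the assumption would become that the i-view is 5 points better.

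Two cautions stand. The equal-rate powers rest on scenarios the plan does not adopt. The figure of 110 per device is approximate, because clinicians decide whether to use VL and may depart from the month's device. Neither affects the result at the stated rates.

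**Conclusion.** The concern holds, and B8.1 must be corrected. At its own inputs the chance of declaring non-inferiority is about 5%, not 80%, at 122, at 220 or at any other total. This follows from the stated rates and margin alone, with the margin read as absolute, as the planned risk-difference test implies. A relative margin makes it worse.

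The reversed-rates explanation is inference, and even under it 122 in total gives 54%. The remaining power figures assume a one-sided 5% test, equal arms and no month-level clustering. With the error rate held at 5%, positive clustering would lower the equal-rate figures.

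**What to change.** Withdraw the statement that 122 in total gives 80% power. Check the original SAS input and state which rates, which margin direction and which size (per device or total) were intended. Then rewrite B8.1 on the accrual basis of B5.2.2, for example:

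> All VL encounters over 2 years will be included, expected about 220 (200 × 55% × 2), or about 110 per device. Non-inferiority is shown if i-view minus reusable first-pass success is above −5 points (Farrington-Manning, one-sided 5%). Power is about 37% if both true rates are 92%, 29% if both are 87%, and 5% at 87% against 92%. These figures assume equal arms and no month-level clustering; with the error rate held at 5%, positive clustering would lower the equal-rate figures.

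If the reversed rates were intended and can be justified, add that power is about 76% at 92% (i-view) against 87% (reusable), and that 80% would need 244 in total.

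The correction itself requires no extra enrolment and no change to the margin, test or data collection. If 87% against 92% really is the expectation, however, those rates and a 5-point margin cannot both stand beside a claim of 80% power, and the investigators must say how they resolve this. The cost is one check of the software input and one rewritten paragraph. The drawback is a much lower stated power, which they will have to defend to their reviewers.

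### At the plan's own first-pass rates, a median and interquartile range for number of attempts will read 1 (1–1) in both groups, and the accompanying Wilcoxon test has only about 24% power, so a null result could be misread as similarity

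*Combined protocol and SAP*

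**What the plan says.** B4 lists two research questions. The second is "Does the i-view have similar attempts required for placement compared to the reusable VL devices". No margin or definition of similarity is attached to it.

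B5.8.2 (Data analysis) applies the Farrington-Manning non-inferiority test to two hypotheses, hypoxic events and first-pass success. Attempts is not among them and is not named anywhere in that section, so it falls under the generic rules. These present "non-parametric continuous variables and ordinal variables as medians and interquartile ranges" and compare such variables by the Wilcoxon rank sum test at the 0.05 level.

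B8.1 gives the planning rates: "the expected outcome rate (proportion of patients experiencing first-pass success) for the i-view is 87%, the expected outcome rate for the reusable VL is 92"%. There is no power statement for attempts.

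**The concern.** Number of attempts is a small count with a floor of 1, and the plan expects about nine patients in ten to sit on that floor. Quartiles of such a variable carry almost no information, and a rank test on it is dominated by ties. The likely report for question 2 is 1 (1–1) v 1 (1–1) with a non-significant p-value. Because the question is framed as similarity and no criterion for it is given, that output invites a conclusion that the data may not support.

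What attempts can add to first-pass success is what happens after the first attempt fails. The planned summary would not show this, although C8.1 lists multiple intubation attempts among the expected adverse events of the procedure.

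**Working it through.** **Plan's own figure.** The documents give no figure for attempts. The total of 122 in B8.1 concerns first-pass success and is used here only as a smaller group size to try (61 per group if split equally).

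**Inputs**
- P(attempts = 1): 0.87 for i-view and 0.92 for reusable (B8.1).
- Group size: 200 intubations × 0.55 × 2 years = 220 (B5.2.2), so about 110 per group. The equal split is an assumption based on alternating months.
- Two-sided 0.05 for the Wilcoxon test (assumed; B5.8.2 gives only 0.05).
- Distribution of later attempts: not in the documents, so a range is shown.

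**Step 1: the summary.** With linear interpolation, the upper quartile of 110 values is 1 if at least 83 of them are 1; for 61 values, at least 46. If X is binomial (n, p):

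| True first-pass success | P(upper quartile = 1), n = 110 | n = 61 |
|---|---|---|
| 92% | >0.999 | >0.999 |
| 87% | 0.9997 | 0.996 |
| 80% | 0.90 | 0.85 |
| 75% | 0.51 | 0.54 |
| 70% | 0.13 | 0.22 |

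The median is 1 in all these cases with probability above 0.999. At 87% and 92%, both groups therefore read 1 (1–1) with probability above 0.999 at 110 per group and 0.996 at 61 per group.

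**Step 2: power of the Wilcoxon test against 92%.** Simulated with tie-corrected variance, 110 per group, and each later attempt succeeding at the same rate as the first:

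| i-view first-pass success | Power |
|---|---|
| 87% | 0.23 |
| 82% | 0.62 |
| 77% | 0.90 |
| 70% | 0.995 |

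At 87%, varying the i-view second-attempt success rate from 50% to 92% moves power only between 0.26 and 0.22. At 61 per group it is 0.14.

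**Step 3: what the test responds to.** Rejection rates at 110 per group for assumed distributions of 1 / 2 / 3+ attempts, in per cent (simulation, accurate to about 1 to 2 points):

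| i-view v reusable | Wilcoxon | Chi-square on 3+ | Fisher on 3+ |
|---|---|---|---|
| 87/10/3 v 92/7/1 | 24 | 15 | 4 |
| 77/20/3 v 92/7/1 | 89 | 15 | 4 |
| 87/4/9 v 92/7/1 | 26 | 83 | 74 |
| 92/1/7 v 92/7/1 | 5 | 64 | 50 |

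In the last row first-pass success is equal and only the split after failure differs. The Wilcoxon test then rejects at its false-positive rate. Across scenarios its rejection rate stays close to that of a chi-square on more than one attempt (for example 26% v 23%, and 62% v 62%).

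**Step 4: what an interval would show.** At the planning rates, more than one attempt occurs in 13% v 8%, a difference of 5 points. SE = √(0.13 × 0.87/110 + 0.08 × 0.92/110) = 0.041, so the 95% interval is 5 ± 1.96 × 4.1, or about −3 to +13 points. For three or more attempts at 3% v 1%, SE = √(0.03 × 0.97/110 + 0.01 × 0.99/110) = 0.019, a half-width of about 3.7 points. That second interval is only a guide, because about one event is expected in the reusable group.

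**The case against.** The strongest reply has four parts.

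- **The test is not inert.** A reader might infer that the summary is 1 (1–1) whatever the device does, or that similarity is built in. The documents do not support this. The upper quartile leaves 1 once first-pass success nears 75%, and B5.8.2 also provides the Wilcoxon test, which has about 89% power at 77% v 92%. A clearly worse device would usually be detected. This stands.
- **More than one attempt is already covered.** It is essentially the complement of first-pass success, which receives a Farrington-Manning risk difference with a confidence interval. This also stands: what the planned analysis loses is mainly the split between two attempts and three or more. But it also means that question 2, as planned, largely repeats question 1 without its margin.
- **The rule is inferred.** B5.8.2 does not assign attempts to the ordinal class, and a mean with a 95% interval is not excluded. This is true, but median and interquartile range is the natural reading for a skewed count, and the ambiguity is itself a reason to name the variable.
- **Three or more attempts is no better as the main contrast.** A reader might infer this from the 87/4/9 row in the working. That result depends on one extreme assumed distribution. Under 87/10/3 v 92/7/1 the 3+ comparison has 15% power (Fisher 4%) against 24% for Wilcoxon, and under 77/20/3 v 92/7/1 it has 15% against 89%. This stands, and it shapes the fix.

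**Conclusion.** The concern holds in a limited form. At 87% and 92% first-pass success, the summary that B5.8.2 most naturally assigns to attempts is uninformative with probability above 99.9% at 110 per group (0.996 at 61). The only test has about 24% power for the 5-point difference that the plan assumes. A true deficit of that size would therefore be non-significant about three times in four, beside identical summaries.

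The summary result rests on the planning rates and on reading attempts as an ordinal or non-parametric variable. The power figures also rest on equal groups, a two-sided 0.05 test and assumed distributions of later attempts, although power at 87% v 92% hardly changes across the range tried. The near-blindness to a shift from two to three or more attempts is shown at equal 92% first-pass success under one assumed split.

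The point concerns how question 2 is reported and interpreted. It does not show that a materially worse device would be missed.

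**What to change.** In B5.8.2, name number of attempts and specify:

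1. The full distribution by device (1, 2, 3 or more), as counts and percentages, in place of median and interquartile range.
2. The risk difference with confidence interval for more than one attempt and, as a descriptive result, for three or more.
3. The Wilcoxon rank sum test retained as the overall comparison, with a sentence stating that a non-significant p-value is not evidence of similarity.

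The cost is wording only, since the count is already needed to answer question 2. The small downside is that three or more attempts is a rare category. Its interval will be wide and should be reported as such, and it should not become the sole or main contrast.

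### Binary outcomes other than first-pass success and hypoxic events get only a chi-square test of difference, with no effect estimate or interval, which cannot support a statement of similarity

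*Combined protocol and SAP*

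**What the plan says.** B5.8.2 treats binary outcomes in two ways.

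- Two outcomes have a named method: "We will use the Farrington-Manning score test for non-inferiority to test the first two hypotheses". These are hypoxic events and first-pass success, and each gets a risk difference with a 90% confidence interval.
- For the rest, the general rule is "We will compare binomial variables using the Chi-square test", with significance at 0.05. The presentation rule is "nominal variables as percentages and numbers". The same sentence plans 95% intervals for means of continuous variables but none for proportions.

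An adjusted estimate is possible but not promised: "we may perform regression modeling to adjust for confounders". No outcome or covariate is named for it.

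The general rule covers several outcomes that matter. The data collection appendix lists, as yes/no items, cardiac arrest and death in the first hour, death before discharge, death in the ICU, and new pneumothorax or pneumonia on chest film. B5.4 says that complications are recorded on the case report form.

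The aim is framed as similarity. B2 closes by asking whether the i-view performs similarly in emergency airway management, and the first question in B4 is "Does the i-view have similar first pass success rates compared to the reusable VL devices".

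**The concern.** A chi-square test asks whether the data contradict equality. Failing to contradict equality is weak evidence when events are few, and it puts no limit on how much worse one device could be. A study that asks whether a cheaper device performs similarly needs the size of the difference and the range of differences that the data still allow. For the outcomes under the general rule, the plan supplies neither.

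These include the most serious events in the dataset. Section C7, on data and safety monitoring, is marked not applicable, so the end-of-study comparison is the only planned comparison of these events between devices. If it yields p>0.05 and two percentages, readers may take the devices to be equally safe when the data cannot exclude a material excess.

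**Working it through.** **The plan's own figure.** There is none for these outcomes. B8.1 gives a total of 122, but for non-inferiority on first-pass success. It does not follow from its stated inputs, because the expected difference (87% − 92% = −5 points) lies on the 5-point margin. That is a separate matter; 122 is used below only as a lower sample size.

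**Inputs from the documents**
- Accrual (B5.2.2): about 200 intubations a year, 55% by video laryngoscopy, for 2 years: 200 × 0.55 × 2 = 220.
- Allocation (B5.3): alternating months, taken as an even split, so n = 110 per device (61 if the total is 122).
- Test (B5.8.2): Pearson chi-square at 0.05, taken as two-sided and uncorrected, since the plan does not say.

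**Assumed input.** Baseline complication rates, from 2% to 20%, because the documents give none.

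**Step 1: how often a true doubling is non-significant.** For x and y events among n per device, with p̄ = (x + y)/2n,

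χ² = ((x − y)/n)² / (2p̄(1 − p̄)/n).

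The probability of p>0.05 is the sum of Bin(x; n, p₁) × Bin(y; n, p₂) over all pairs with χ² below 3.84.

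| True rates, reusable → i-view | p>0.05, 110 per device | p>0.05, 61 per device |
|---|---|---|
| 2% → 4% | 88% | 93% |
| 5% → 10% | 70% | 82% |
| 10% → 20% | 44% | 67% |
| 15% → 30% | 23% | 48% |
| 20% → 40% | 9% | 32% |

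Check by normal approximation for 5% → 10% at 110:
- √(2 × 0.075 × 0.925) = 0.3725
- √(0.05 × 0.95 + 0.10 × 0.90) = 0.3708
- z = (0.05 × √110 − 1.96 × 0.3725)/0.3708 = −0.55
- power ≈ 29%, against 29.8% by enumeration.

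With a continuity correction, power for that row falls to 19.7%, so 80% of trials would be non-significant.

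**Step 2: sample size for 80% power.** For 5% → 10%, n = ((1.96 × 0.3725 + 0.84 × 0.3708)/0.05)² ≈ 435 per device, or 870 in total. For 10% → 20% the same formula gives 398 in total. Both exceed 220.

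**Step 3: what an interval would add.** Suppose 10 of 110 events with the i-view and 5 of 110 with reusable devices.
- Chi-square: p = 0.18.
- Risk difference: 9.09% − 4.55% = 4.55 points.
- Wilson 95% limits: 5.0% to 15.9% and 2.0% to 10.2%.
- Newcombe lower limit: 4.55 − √(4.08² + 5.66²) = −2.4 points.
- Newcombe upper limit: 4.55 + √(6.84² + 2.59²) = 11.9 points.

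The p-value alone reads as no significant difference. The interval shows that an excess of almost 12 points is not excluded.

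**The case against.** Several points on the other side stand.

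- A reader might infer that the plan will treat p>0.05 as proof of similarity. No section says so. The two questions in B4 that use the word concern first-pass success, which has a non-inferiority test, and number of attempts, which is not binary. The broader aim in B2 does reach overall performance, but the misreading remains a risk and not a stated rule.
- A reader might infer that the chi-square sentence gives first-pass success a second route to similarity if non-inferiority fails. The sentence has no exception, but B5.8.2 names a specific test for that outcome, and a specific rule ordinarily governs a general one. This is an ambiguity to close, not a planned second analysis.
- A reader might set the interval's width against the 5-point margin. With 5% in both groups at 110 each, the 95% half-width is 1.96 × √(2 × 0.05 × 0.95/110) = 5.8 points. But the margin is stated for first-pass success, and the plan pairs its non-inferiority test with a 90% interval, whose half-width here would be 1.645 × the same root = 4.8 points. The comparison proves nothing.
- Counts are reported with percentages, so a reader could derive an interval, and regression may add an estimate. Neither is a commitment to report one.
- The complications named in C8.1 ("hypoxia, aspiration, dental or other oral injury, multiple intubation attempts, false intubation into the esophagus") illustrate expected events; they are not a list of endpoints. Hypoxia has its own test.
- Common complications are less exposed: at 110 per device, power for a doubling is 77% from a 15% baseline and 91% from 20%.

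**Conclusion.** The point holds as a gap in estimation and reporting for the binary outcomes without a non-inferiority test. They get a test of difference and no planned effect estimate or interval, in a study whose aim is similarity. At about 110 per device a true doubling would be non-significant in 88%, 70% and 44% of trials from baselines of 2%, 5% and 10%, falling to 23% at 15% and 9% at 20%. The conclusion is therefore strongest for uncommon events.

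These figures rest on assumed baseline rates, an even split, complete data, an uncorrected two-sided test and independent encounters; clustering by month or operator is ignored. The documents do not support saying that the plan will call the devices similar on the strength of p>0.05, only that it provides nothing better for these outcomes. The non-inferiority analyses of first-pass success and hypoxic events are unaffected.

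**What to change.** In B5.8.2:

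1. For each binary outcome other than first-pass success and hypoxic events, report the risk difference (i-view minus reusable) with a 95% score interval (Miettinen-Nurminen or Newcombe), beside the counts and percentages and in place of a stand-alone chi-square p-value.
2. State that p>0.05 will not be described as showing that the devices are similar.
3. State that the Farrington-Manning test with its 90% interval is the only comparison of first-pass success and hypoxic events, and that the chi-square sentence does not apply to them. This also settles which interval level belongs to which outcome.

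The cost is a few sentences and a few more table columns, with no extra patients or data. The drawback is that the intervals will be wide, so the safety statement will look less favourable than a row of non-significant p-values.
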